5.3.1.2 Collection and Handling of Exploratory Research Samples

Exploratory Research Samples

Subjects will have the option to provide samples for exploratory research. Subjects may still participate in the main study even if they decide not to participate in this optional exploratory research.

AbbVie (or people or companies working with AbbVie) will store the exploratory research samples in a secure storage space with adequate measures to protect confidentiality. The samples will be retained while research on elagolix (or drugs of this class) or this disease and related conditions continues, but for no longer than 20 years after study completion. The procedure for obtaining and documenting informed consent

(via a separate consent document) for exploratory research samples is discussed in Section 9.3.

Samples for Pharmacogenetic Exploratory Research

[figure not shown]
Two optional whole blood samples, one for DNA and a second for RNA will be collected on Day 1, Month 6, Month 12 and Premature Discontinuation Visit (if applicable) from each subject who consents to provide samples for exploratory research. An endometrial sample for pharmacogenetic testing will be collected during Screening and at Month 12 for each subject who consents to provide samples for exploratory research.

Samples will be shipped frozen to AbbVie or a designated laboratory for DNA and RNA extraction and long-term storage. Instructions for the preparation and shipment of the pharmacogenetic exploratory research samples will be provided in a study-specific laboratory manual.

5.3.1.3 Collection and Handling of Pharmacodynamic Variables

A single blood sample will be collected at each timepoint as indicated in Appendix C to be used for the analysis of estradiol and potentially for additional testing (e.g., re-testing of hormone levels with an alternative methodology or for testing and potential validation of exploratory biomarkers for endometriosis). The blood samples for assay of estradiol will be collected by venipuncture in one 7 mL evacuated collection tube without anticoagulant (red cap, no gel separators to be used). Sufficient blood volume will be collected to provide approximately 3 mL serum from each sample. Refer to the study specific laboratory manual for detailed instructions on sample collection, processing and shipment.

The date and time of collection will be recorded in the source documentation. The Day 1 sample will be obtained pre-dose; samples collected at all other visits can be drawn at any time during the visit.

5.3.2 Drug Concentration Measurements

5.3.2.1 Collection of Samples for Analysis

Blood Samples for Elagolix and Norethindrone Assay

Blood samples for assay of elagolix and norethindrone (PK samples) will be collected by venipuncture into 4 mL evacuated K₂-ethylenediaminetetraacetic acid (K₂EDTA)-containing collection tubes at the times indicated in Appendix C. Sufficient blood will be collected to provide approximately 2 mL plasma from each sample. Refer to the study specific laboratory manual for detailed instructions on sample collection, processing and shipment.

Samples will be collected regardless of the time of last dose. The date and time of collection will be recorded in the lab requisition form.

5.3.2.2 Measurement Methods

Plasma concentrations of elagolix and norethindrone and serum concentrations of estradiol will be determined using validated methods by the Bioanalysis Department at AbbVie. Plasma or serum concentrations of other possible metabolites may be determined with validated or non-validated methods.

5.3.3 Efficacy Variables

5.3.3.1 Primary Variables

The co-primary efficacy endpoints will be the proportion of responders at Month 6 based upon the mutually-exclusive scales for daily assessment of DYS and NMPP measured by the 4-point Endometriosis Daily Pain Impact Diary. Use of protocol specific analgesic medication for endometriosis-associated pain will also be included in the responder definition. The comparison is between the elagolix plus E2/NETA group and placebo group.

5.3.3.2 Secondary Variables

The key secondary measures of the Treatment Period that will be tested will include the following:

- Change from baseline in Overall Endometriosis-Associated Pain at Month 3, Month 6, and Month 12
- Change from baseline in DYS at Month 3, Month 6, and Month 12
- Change from baseline in NMPP at Month 3, Month 6, and Month 12
- Change from baseline in dyspareunia at Month 3, Month 6, and Month 12
- Change from baseline in PROMIS Fatigue Short Form 6a T-Score at Month 6 and 12

5.3.3.3 Additional Efficacy Variables

The following efficacy variables will be collected during the treatment period:

- Proportion of responders as assessed by change from Baseline in average pain score and analgesic use monthly for DYS, NMPP and dyspareunia, respectively.
- Proportion of responders as assessed by change from Baseline in average pain score alone (i.e., not taking into consideration of analgesic use) monthly for DYS, NMPP and dyspareunia, respectively.
- Change from Baseline, in the monthly average pain score (DYS, NMPP, and dyspareunia), as assessed using information from the e-Diary.
- Change from Baseline in analgesic use (average pill counts) to treat endometriosis-related pain, as assessed using information from the e-Diary monthly.
- Proportion of analgesic use responders monthly (based only on reduction of rescue analgesics used).
- Monthly response in the PGIC and overall endometriosis-associated pain questionnaire.
- Change from baseline for each of six domains of EHP-30 questionnaire scores.

- Change from baseline for the EuroQoL-5D (EQ-5D-5L).
- Change from baseline for the WPAI:SHP.
- HCRU at each scheduled assessment.
- Change from baseline for the PROMIS Fatigue short Form 6A T-Score.

5.3.4 Safety Variables

- Bone mineral density and percentage change from baseline measured by DXA
- Summary of hypoestrogenic adverse events
- Proportion of subjects reporting adverse events
- Time to the first post-treatment menses
- Uterine bleeding measured by e-Diary
- Clinical laboratory parameters
- Vital signs and body weight
- Endometrial biopsy and TVU findings

5.3.5 Pharmacodynamic Variables

Concentrations of estradiol will be obtained throughout the Treatment Period. Additional pharmacodynamic parameters may be calculated if useful in the interpretation of the data.

5.3.6 Pharmacokinetic Variables

Exposures of elagolix and norethindrone will be summarized and elagolix concentrations may be used to develop a population pharmacokinetic model. Additional parameters may be calculated if useful in the interpretation of the data.

5.3.7 Exploratory Research Variables

Exploratory Research Variables

Optional samples may be collected to conduct exploratory investigations into known and novel biomarkers. The types of biomarkers to be analyzed may include, but are not

limited to, nucleic acids, proteins, lipids, metabolites or hormone concentrations (estradiol). The samples may be analyzed as part of a multi-study assessment of factors influencing the subjects' response to the study drug (or drugs of the same or similar class) or the development and progression of the subjects' disease or related conditions. The samples may also be used to develop new diagnostic tests, therapies, research methods or technologies. The results from these analyses are exploratory in nature and may not be included with the study report.

5.4 Removal of Subjects from Therapy or Assessment

Each subject has the right to withdraw from the study at any time. In addition, the Investigator may discontinue a subject from the study at any time if the Investigator considers it necessary for any reason, including the occurrence of an adverse event or noncompliance with the protocol. Subjects who withdraw from the study will not be replaced unless it is mutually agreed upon, in writing, by the Investigator and AbbVie. Subjects will be withdrawn from study drug treatment and/or the study if any of the following occur:

- The subject decides to withdraw consent for any reason
- The investigator believes it is in the best interest of the subject
- Clinically significant deterioration of the subject's medical status as determined by the Investigator
- The subject becomes pregnant or subject has a positive serum pregnancy test
- The subject has ALT or AST elevation > 5 times the upper limit of normal, confirmed upon repeat testing
- The subject develops clinically significant gynecological findings or condition on either the TVU (confirmed by repeat TVU and/or SIS and/or office hysteroscopy) or endometrial biopsy that in the opinion of the Investigator or AbbVie TA MD would preclude the subject from continuing in the Treatment Period due to safety reasons
- The results of any post-baseline DXA prior to Month 48 document a Z-score (for subjects ≤ 40 years of age) or T-score (for subjects ≥ 40 years of age) of

- < -2.5, a BMD decrease from baseline of > 8% in the lumbar spine, total hip or femoral neck, or due to TA MD assessment when the BMD percent change from baseline cannot be provided by the central reader
- The subject will require ongoing use of prohibited medications to manage or treat her endometriosis or endometriosis-associated pain in the opinion of the Investigator or AbbVie TA MD
- The subject requires use of prohibited medications to manage or treat bone mineral density changes during the Treatment Period as described in Section 5.2.3.3. Subject continuation in the Follow-Up Period is at the discretion of the AbbVie TA MD.
- The subject requires surgical intervention for treatment of endometriosis or uterine bleeding (e.g., laparoscopy, hysterectomy, ovarian cystectomy)
- The Investigator and AbbVie TA MD deems it appropriate to protect the subject because the subject expresses suicidal ideation on the C-SSRS or via clinical interview at any time during the study.
- In the Investigator's opinion, the subject is unable or unwilling to comply with study-related assessments and procedures, including completion of the e-Diary
- Any other medical reason that AbbVie or the Investigator deems appropriate.

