5.2 Selection of Study Population

5.2.1 Inclusion Criteria

[figure not shown]
- 1. Subject has voluntarily signed and dated the informed consent form (ICF), approved by an Institutional Review Board/Ethics Committee (IRB/EC), prior to washout (if applicable), or initiation of any screening or study-specific procedures.
- 2. Subject is a premenopausal female 18 to 49 years of age (inclusive) at the time of Screening.

- 3. Subject has a documented surgical diagnosis (e.g., laparoscopy or laparotomy) of endometriosis established by visualization or histology within 10 years prior to entry into Washout or Screening.
- 4. Subject must agree to use only those rescue analgesics permitted by the protocol during the Screening and Treatment Periods for her endometriosis-associated pain.
- 5. Subject must have a negative urine and/or serum pregnancy test(s) during the Washout (if applicable) and/or Screening Periods, and a negative urine pregnancy test just prior to administration of the first dose of study drug.
- 6. Subject must agree to use two forms of non-hormonal contraception (dual contraception) consistently during the Washout (if applicable), Screening, Treatment and through the end of Month 1 of the Follow-Up Period. Acceptable methods of dual contraception include the following combinations:
 - Condom with spermicide (e.g., cream, spray, foam, gel, suppository or polymer film)
 - Diaphragm with spermicide (condom may or may not be used)
 - Cervical cap with spermicide (condom may or may not be used)
 - Vaginal sponge impregnated with spermicide and used with a condom.

Subject is not required to use dual contraception methods if:

- Sexual partner(s) is (are) vasectomized, at least 6 months prior to Screening
- Subject practices total abstinence from sexual intercourse as the preferred lifestyle of the subject; periodic abstinence is not acceptable and requires use of dual contraception.
- Subject had a bilateral tubal ligation or bilateral tubal occlusion at least 4 months prior to the start of Screening
- Subject is not sexually active with men; however, periodic sexual relationship(s) with men require the use of study defined dual non-hormonal contraception.

- 7. Subject ≥ 40 years of age at entry into screening has a normal mammogram during Screening or within 3 months prior to the start of Screening (BI-RADS Classification 1 to 3 or equivalent).

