Subjects will be asked about post-treatment to menses using the Return to Menses Questionnaire (Appendix H) in the Follow-Up Period, as outlined in Appendix C. Site staff will ask subjects if they have had a menstrual period since discontinuation of study drug and record subjects' responses directly onto the paper questionnaire (which will then be entered into the eCRF). If the subject indicates she has not returned to menses, site staff will continue to assess return to menstruation and repeat the questionnaire at subsequent follow-up visits, as applicable. The date when menses returned will be documented in the source documents and eCRFs.

Assignment of Subject Numbers

The site will contact the Interactive Response Technology (IRT) during the Washout or Screening Period to obtain a subject (Screening) number after the subject has signed the informed consent. Consecutive and unique subject numbers within each site will be assigned. The same subject number will be used to identify the subject throughout the study (Screening, Treatment and Follow-Up Periods). If the subject is not randomized into the study on Day 1, the reason for screen failure will be documented in the eCRF and the site will register the subject as a screen failure in IRT.

Randomization/Study Drug Kit Assignment

Subjects are to be randomized between Cycle Days 1-10 of her menstrual cycle (Cycle Day 1 is defined as the first day with full menstrual flow); however, randomizations beyond Day 10 of the subject's menstrual cycle must be discussed with the AbbVie TA MD prior to randomizing the subject and will be evaluated on a case by case basis, including whether additional procedures are required.

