5.4.1 Discontinuation of Individual Subjects

In the event that a subject withdraws or is prematurely discontinued from study drug treatment, the subject should complete the Premature Discontinuation Visit as soon as possible (preferably within 2 – 7 days after last dose of study drug, if possible) and undergo study procedures as outlined in Appendix C. These procedures should not interfere with the initiation of any new treatments or therapeutic modalities the Investigator determines are necessary to treat the subject's condition. The reason(s) for the discontinuation from the Treatment Period will be recorded. Subjects who prematurely discontinue at the time of or after the Month 6 visit during the Treatment Period are expected to enter the Follow-Up Period for 12 months unless discontinuing due to pregnancy.

If a subject becomes pregnant during the Treatment Period or within 30 days of the last dose of study drug, no additional study procedures, except an ultrasound will be conducted. Refer to Section 6.1.4 for instructions on reporting of a pregnancy to the Sponsor and the required follow-up on the subject and fetus/infant.

If a subject requires surgery (e.g., laparoscopy, hysterectomy, ovarian cystectomy) for the management of their endometriosis during the Treatment Period, study drug should be discontinued and the Premature Discontinuation visit should be completed prior to surgery, if possible.

If a subject is discontinued from the study with an ongoing adverse event or an unresolved laboratory result that is clinically significant (as determined by the Investigator), the Investigator will attempt to provide follow-up until a satisfactory clinical resolution of the laboratory result or adverse event is achieved.

If a subject is being discontinued from the study prior to the completion of Treatment Month 6 time point, a mammogram (only for subjects \geq 40 years of age), DXA, TVU, Pap test, or endometrial biopsy does not need to be performed.

In addition, if a subject is being discontinued from the study due to a documented Z-score or T-score result of < -2.5, BMD decrease from baseline of > 8%, or TA MD assessment, an additional DXA scan does not need to be performed as a part of the Premature Discontinuation visit procedures.

Upon discontinuation from the Treatment Period, all used and unused study drug containers should be returned to the study site.

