- 1. Urine pregnancy tests will be self-administered at home by the study subject at Treatment Months 7, 9, 11, 13 14, 16 17, 19 20 and 22 23, 25 26, 28 29, 31 32, 34 35, 37 38, 40 41, 43 44, and 46 47. Subjects will self-administer the at home urine pregnancy tests (kits provided by the central laboratory) and report the results to the site at the phone contact visits. A positive urine pregnancy test result must be confirmed with a serum pregnancy test.
- m. A negative urine pregnancy result should be obtained on the day of the endometrial biopsy, prior to performing the procedure. Prior to Month 36 an endometrial biopsy is not required if the TVU findings at the PD visit indicate an endometrial thickness <4 mm. If the TVU findings indicate an endometrial thickness ≥ 4 mm, then the subject must have an endometrial biopsy performed. Endometrial biopsy at Month 36 or 48 (or PD after Month 36 if needed) will be performed regardless of TVU finding at the corresponding visit.
- n. Optional urine test for gonorrhea/chlamydia should be performed prior to undergoing the endometrial biopsy. Positive test results will be treated outside of the protocol.
- o. On Day 1, the Pharmacodynamic sample should be collected with the safety labs prior to dosing.
- p. Overall endometriosis-associated pain will be assessed via an 11-point numeric rating scale (NRS [0-10]) that will be administered to the subject by site staff.
- q. Premature Discontinuation prior to the time of the Treatment Month 6 visit or within six months of a mammogram, DXA, TVU, Pap test, or endometrial biopsy does not require a mammogram, DXA, TVU, Pap test, or endometrial biopsy.
- r. If the subject prematurely discontinues, the site should counsel the subject on the continued use of non-hormonal contraceptive use for at least 30 days after the last dose of study drug.

Study Activities – Follow-Up Period

[figure not shown]
	Follow-Up Period ^a			
Activity	Month 1	Month 6	Month 12	
DXA		X ^b	Xb	
Physical Exam ^c	X			
Estradiol (E2) sample	X	X	X	
FSH sample	X			
Pregnancy Test	$X^{d}\left(u,s\right)$	X ^e (u)	Xe (u)	
Review Adverse Events	X ^f	X ^g	Xg	
Concomitant Medication	Xe	X	X	
Return to Menses Questionnaire ^h	X ⁱ			

- a. All subjects will complete a 12 month Follow-Up Period after the last Treatment Month 48 Visit.

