9.5.5 Post-treatment Assessment of Menstruation

Time to first post-treatment menses will be summarized based on 28-day windows during the Follow-up Period: Study End Days 1 – 28, 29 – 56, 57 – 84, 85 – 112, 113 – 140, 141 – 168, and ≥ 169 . The number and percentage of subjects by who answered "Yes" to the question "Has the subject had a menstrual period since stopping study drug" with an onset date fall into the above time interval will be summarized by treatment group. The denominator is the number of subjects who answered the follow-up assessment of menstruation eCRF at each time interval.

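### The return-to-menses denominator in SAP 9.5.5 includes women who can no longer menstruate, which lowers the reported percentage resuming menses by an unknown and possibly small amount

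*Protocol*

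**What the plan says.** The rule that matters is in SAP 9.5.5. It tabulates women who report a first post-treatment period by 28-day window of onset, and adds: "The denominator is the number of subjects who answered the follow-up assessment of menstruation eCRF at each time interval". It has no exclusion, censoring or separate category. Protocol 8.1.7.5 says only that the timing will be summarized.

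Three sets of provisions determine who is in that denominator.

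- **Surgery.** Protocol 5.4 gives as a reason for withdrawal: "The subject requires surgical intervention for treatment of endometriosis or uterine bleeding (e.g., laparoscopy, hysterectomy, ovarian cystectomy". Its scope is: "Subjects will be withdrawn from study drug treatment and/or the study if any of the following occur". For surgery, Protocol 5.4.1 states that "study drug should be discontinued and the Premature Discontinuation visit should be completed prior to surgery, if possible". Those who stop at or after the Month 6 visit "are expected to enter the Follow-Up Period for 12 months unless discontinuing due to pregnancy".
- **Age.** Protocol 5.2.1 admits a "premenopausal female 18 to 49 years of age (inclusive) at the time of Screening". This is an entry criterion only; menopause is not a removal criterion in 5.4. For women who finish treatment, the Follow-Up table in Protocol Appendix C says: "All subjects will complete a 12 month Follow-Up Period after the last Treatment Month 48 Visit".
- **The form.** The questionnaire in Protocol Appendix H has a Yes box and a No box, with no option for surgery or menopause. After a No, Protocol 5.3.1.1 continues: "If the subject indicates she has not returned to menses, site staff will continue to assess return to menstruation". The question is put again at Follow-Up Months 6 and 12.

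Appendix C schedules an FSH sample at Follow-Up Month 1. SAP 9.5.5 makes no use of it.

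**The concern.** Time to first post-treatment menses is a listed safety variable (Protocol 5.3.4). The question it should answer is how soon, and how often, menses return in women who are able to menstruate. The denominator does not restrict itself to them. A woman whose uterus was removed before any post-treatment period, or who passed menopause during treatment, cannot move from No to Yes, yet she stays among those counted.

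For safety, the part of this table that matters is the small group whose menses have not come back. Women who cannot menstruate collect in exactly that group, so even a few of them can weigh heavily there. No one stays on placebo after Month 12, so for most women in Follow-Up there is no untreated group in which the same error would show. The percentage will largely be read as an absolute rate.

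**Working it through.** The plan states no figure for return to menses, hysterectomy or menopause on study, so there is nothing to reproduce. The check has three steps.

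**1. Can such women reach the denominator?** By the rules above, a woman withdrawn for hysterectomy at or after Month 6 is expected in Follow-Up and is asked the question. If she had no period between last dose and surgery, the true answer is No at every visit.

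**2. Can menopause occur on study?** Inputs: entry before the 50th birthday (Protocol 5.2.1), a 28-day month (Protocol 1.3), 48 months of treatment, 12 of Follow-Up, and up to 4 months of Screening, taken here as 4 × 28 = 112 days.

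- Treatment: 48 × 28 = 1,344 days; 1,344 / 365.25 = 3.68 years.
- Oldest possible age at end of treatment: 49.99 + (112 + 1,344) / 365.25 = 54.0 years.
- At Follow-Up Month 12: 49.99 + (112 + 60 × 28) / 365.25 = 54.9 years.

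Menopause on study is therefore possible. Protocol 3.4 notes that elagolix can itself cause amenorrhea, so menopause may go unnoticed during treatment.

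**3. How large is the effect?** Let h be the share of women answering the form who cannot menstruate and have had no post-treatment period, and r the return rate in the others. Both are assumptions.

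- Reported return = r(1 − h)
- Implied non-return = 1 − r(1 − h)
- Non-return among women able to menstruate = 1 − r
- Excess = r × h

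| r | Non-return in women able to menstruate | Implied, h = 0.5% | Implied, h = 2% | Implied, h = 5% |
|---|---|---|---|---|
| 80% | 20.0% | 20.4% | 21.6% | 24.0% |
| 90% | 10.0% | 10.5% | 11.8% | 14.5% |
| 95% | 5.0% | 5.5% | 6.9% | 9.8% |
| 98% | 2.0% | 2.5% | 4.0% | 6.9% |

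The excess runs from 0.80 × 0.005 = 0.4 points to 0.98 × 0.05 = 4.9 points. In relative terms the implied non-return is 20.4 / 20.0 = 1.02 to 6.9 / 2.0 = 3.45 times the figure for women able to menstruate.

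The denominator is also ambiguous. The form is completed at Follow-Up Months 1, 6 and 12, but the windows are 28 days long, so who has answered in a given interval is not settled. If later denominators hold only women still answering No, those unable to menstruate are h / (1 − r(1 − h)) of them. With r = 95% and h = 2% that is 0.02 / 0.069 = 29%.

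**The case against.** Much can be said on the other side, and most of it limits the point without removing it.

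- **There is no planned non-return result.** SAP 9.5.5 has no such row, rate or test; non-return is only the complement of the Yes counts. This stands. The percentage resuming is still biased, because its denominator is stated.
- **Not every hysterectomy counts.** Women who stop before Month 6 do not enter Follow-Up, Protocol 5.4 allows withdrawal from the study altogether, and a woman who bled between last dose and surgery correctly answers Yes. This stands and keeps h down.
- **There is an opposite error.** For women without menses at Follow-Up Month 1, Protocol 5.2.4 mentions inducing a withdrawal bleed before hormonal contraception. Recorded as Yes, it would overstate return. So each woman unable to menstruate pulls the percentage down, but the net direction of the table's error is not established.
- **Pregnancy is not a comparable case.** A reader might infer that women who conceive before a first period also stay as failures. Protocol 6.1.6 and the Follow-Up notes in Appendix C discontinue them once pregnancy is confirmed. At most an earlier No remains.
- **The table is descriptive.** True, but it is the only planned analysis of a listed safety variable.

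None of these supplies the missing rule on who is eligible to be counted.

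**Conclusion.** The point holds in a limited form. Followed as written, SAP 9.5.5 keeps in its denominator women who cannot resume menses, and each of them lowers the reported percentage. The size cannot be found from the documents and may be small: 0.4 to 4.9 percentage points if h is 0.5–5% and r is 80–98%, and less if h is lower.

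Two stronger readings are tempting and not supported. One is that non-return would be reported at about twice its true value. That needs particular assumed values (for example h = 2% with r = 98%, giving 4.0% against 2.0%); the same grid goes down to 1.02 times. The other is that the non-return figure would say nothing about the drug. In that same example, 0.98 × (1 − 0.98) = 1.96 points of the 4.0% come from women able to menstruate, about half.

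The efficacy analyses are not affected.

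**What to change.** Amend SAP 9.5.5 as follows.

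1. Exclude women with hysterectomy or bilateral oophorectomy before first post-treatment menses, or censor them at the date of surgery in a time-to-event summary. Censoring keeps the time during which menses could have returned.
2. Show women not returned whose Follow-Up Month 1 FSH is in the laboratory's postmenopausal range in a separate row, and keep them in the overall summary so that no drug effect is hidden.
3. Report the number in each group.
4. Flag medically induced withdrawal bleeds, where recorded, so that they are not counted as spontaneous return.
5. State who forms the denominator in each 28-day window.

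The cost is a paragraph of SAP text and some programming. Reasons for discontinuation are recorded under Protocol 5.4.1, and the FSH sample is already scheduled. There are three drawbacks. The denominator becomes slightly smaller. A single FSH value is only indicative of menopause. Surgery more than 30 days after last dose may be incompletely captured, because Protocol 6.1.4 then collects only serious and bone-related adverse events. The table should carry a note on that last limit.
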